B.5.1.a. Website: The study website developed in Aim 1 will be a centralized information delivery portal that contains: graphical depictions of genetic risk, short videos on hereditary cancer risk, photonovelas, structured interactive Q&A choices highlighting pros and cons of seeking genetic services from the perspectives of survivors, and resources for patient navigation programs near them. On entering the website, survivors will see an explanation of the study and the opportunity to continue or to decline. The online consent form ends with the "I agree" checkbox so the participant can decide whether they still want to participate after reading the listed conditions. [name] successfully used a similar approach with 6,400 enrollees in a managed care organization.⁵⁴ Fully 32% of those who received mailed invitations with log-in information visited the website.⁵⁵ Results showed high levels of information recall and accurate interpretations of the limits of the genetic susceptibility testing for common diseases suggesting this platform enabled informed consent.⁵⁶ The website will ask survivors who log-in to review informed consent information, click the "I agree" button if they want to proceed, and on a separate webpage to complete the requested "*small ask*" task to enumerate their 1st and 2nd-degree relatives (henceforth "close relatives") by first name only and to specify the relationship. Once completed, the survivor will view options for how close relatives might be contacted (we will present 3-4 options that represent graduated involvement of study staff). We will pair each option with personal stories to illustrate pros and cons of the choices. The website will then prompt survivors to complete the "*large ask*" task, which entails selecting an option (e.g., close relatives contacted solely by survivor, share contact of some relatives with study team, study team contact all enumerated relatives, refuse contact, etc.). Survivors who select options that involve the study team reaching out on the survivor's behalf will be prompted to provide contact information (e.g., mailing address, email, phone number) for relatives. Relatives specified for study contact will be sent (via email, mail or text) personal login information linked to the survivor; provide survivors

Figure 3: MBI flow of survivor-relative contact

Survivor receives packet/website login from GCR

"Small ask task"-Login to website and enumerate relatives

- Relative 1: first name, relationship
- Relative 2: first name, relationship
- ...etc

"Large ask task"-Select contact choice for enumerated relatives

- Relative 1: first name, relationship

A. Select willingness to contact:

- Yes, no, will decide later

B. If yes, select contact method:

- Survivor contact only
- Study team contact only
- Survivor and study team
- Other choices developed in Aim 1

C. If agree study team contact, provide relative contact information:

- Mail, email, or phone number
- Relative 2:
- ...etc

Relative receive unique website login depends on contact choice

who opt to contact relatives will be provided with unique log-in information for each of the relatives they list. Relatives that survivors refuse contact will be noted but not contacted.

B.5.1.b. Short messages: Survivors who provide mobile phone numbers will receive two SMS thanking them for accessing the website, and encouraging them to revisit the website to review information and contact relatives. We will time these cues to occur at 3-week intervals over a 6-week time period (two SMS). Additionally, reviews of SMS studies suggest including a substantial pre-testing phase that allows target audiences to provide input on message content as we propose to do in Aim 1.

B.5.1.c. Genetic service options: We will offer free pre-test telegenetic counseling to all survivors who log in to the website, regardless of whether they complete the tasks. Two recent trials showed that similar approaches are non-inferior to face-to-face counseling.^{57,58} Survivors can opt for phone and/or video counseling via Emory HIPPA approved Zoom links. They can schedule a session (~60 min) on the study website by providing their contact information and preferred appointment date/time. We will ask survivors to review an online genetic counseling consent form and complete a brief intake survey (e.g., prior genetic testing result). Survivors may invite a support person or other family members to participate in the session. Scheduling a telegenetic counseling session indicate that participants agree to receive services provided by means of telemedicine by a genetic counselor intern at Emory University. Genetic counseling interns (supervised by Drs. [name] and [name]) will proactively contact consented survivors for the counseling sessions. Interns will be blinded to participant's/relatives study-arm assignment. All interns will have comprehensive training in cancer genetics and use of telemedicine. The intern will be trained in best practices: review personal and family medical history, discuss appropriate genetic tests (e.g., minimum *BRCA* and Lynch syndrome, other genes based on survivors' family history), and discuss the risks/benefits/limitations of recommended tests. Interns also will receive training in how to refer survivors to informational and support resources, including any local patient navigator programs to assist the participant with additional medical care needs. Participants will receive a copy of their pedigree, a medical referral letter summarizing key aspects of the counseling session and recommendations for genetic testing. We will recommend that participants share these letters with their primary care provider (PCP) as follow-up. If participant's prefer, the intern can work with the PCP to arrange genetic testing. We will also offer post-test telegenetic counseling at no cost to all participants. Medicare's covers *BRCA1/2* genetic testing for people with personal history of ovarian cancer. In addition, the Genetic Testing Fund established by Georgia CORE ([name], President and Co-I) provides access to genetic testing for hereditary breast and ovarian cancer for uninsured Georgians.⁵⁹ Since 2014, the Fund has supported testing for over 70 underinsured Georgians who would not have otherwise been able to afford it.

B.5.2. Close relative procedures: Relatives eligible to participate must be: 25 years or older (age recommended to initiate preventive behaviors)⁶⁰, able to access the internet, a 1st or 2nd degree relative of the survivor, able to read English, and non-incarcerated or institutionalized. Relatives will receive a unique website login linked to the survivor that enables access to the website content and describes pros/cons of family-history-based genetic risk screening for HBOC. Additionally, relatives for whom we have cell phone numbers will receive 3 cueing SMS reminders over 9 weeks (developed during Aim 1). The SMS will thank them for visiting the website and

suggest they return as needed and complete the genetic risk assessment for ovarian cancer family history. We will use the B-RST™ (developed and validated by [name] in 2009),^{61,62} which is endorsed by the USPSTF as one of several validated screening tools that is clinically useful for estimating the probability of *BRCA1/2* mutation and identifying women for referral to genetic counseling. This screener assesses personal and family history (1st and 2nd relatives) of breast cancer, bilateral breast cancer, ovarian cancer and male breast cancer, and Ashkenazi Jewish heritage. The intervention website will include a separate portal dedicated to the B-RST™ 3.1 screen. Although all 1st or 2nd degree relatives of ovarian cancer survivors will screen positive on B-RST™, completing the screener will raise participant awareness of the factors that contribute to hereditary risk of ovarian cancer and will reinforce the salience of seeking genetic counseling. We will recommend genetic counseling for all close relatives because of their heightened risk for carrying a *BRCA1/2* mutation. We will direct interested relatives to the same telegenetic counseling services provided to survivors. Ideally, we would recommend testing the survivors first, and only offer genetic testing to close relatives with a confirmed pathogenic variant ala cascade testing. However, we will offer genetic testing to relatives regardless of survivor's testing status.

B.6. Standard Outreach Arm

B.6.1. Survivor components: GCR will mail survivors a standard letter and log-in information. Survivors will have access to a condensed version of the website that includes information on: genetic risk and genetic counseling, patient navigators in their locale, and the importance of conveying information to close relatives. Survivors will be provided with 2 extra letters and login information for 2 close relatives. Survivors can request additional relative letters/logins for any relatives that they would like to involve on the website or the GCR.

B.6.2. Close relative components: The standard family letter shared by the survivor will provide login codes for the relative to visit the condensed website with information about genetic risk and the value of completing the online B-RST™ screener.

All survivors and relatives in the standard arm will have access to the telegenetic counseling services described above. After completion of intervention trial, all survivors in the standard outreach arm regardless of their study participation will have access to the MBI sections of the website.

6.2 *Procedures being performed to monitor participants for safety or minimize risks.*

We expect the research-related risk to be minimal: the probability & magnitude of harm/discomfort anticipated in the research is no greater than those ordinarily encountered in daily life or during the performance of routine physical or psychological examinations/tests.

There are no anticipated physical risks of participating in this study. However, participants may experience psychological or emotional distress from participating in the study, particularly activities related to the way their family interacts or communicates about ovarian cancer and genetic risks. Survivors may worry about their family members' emotional distress. Participants whose motivations for study

enrollment include histories of ovarian cancer in either themselves or their family members may find it upsetting to re-visit their personal experiences.

There is a small potential risk of outreach to family members of a recently deceased woman. In GCR's past experiences, this event does indeed happen on occasion but the typical response is a family member contacts GCR to inform about the passing of their family member. No adverse event has been reported thus far (e.g., distress, confusion). The proposed research activities present the same outreach risk (which is minimal) as routine contact by the GCR.

Other potential risks to participation include the possibility of a breach of confidentiality or data privacy in which the study participant's involvement in genetic counseling, comments or survey information may become known by individuals not directly involved in the research.

In order to attenuate the likelihood and impact of these potential risks:

Throughout recruitment, GCR will perform monthly checks to minimize the risk of initiating contact with a recently deceased woman. If such contact occurs, GCR's standard protocol is that the registry is the single point of contact for all patient outreach. The GCR's primary goal is to ensure that trained registry staff respond to such calls and work to reduce possible distress and address questions and concerns per their standard protocols.

Participants will be informed that their responses will be described in aggregate and they can skip any questions they do not wish to answer, or withdraw from the study at any time. Additionally, all of those who log in to the study website (restricted or expanded) will be provided with a 24-hour call in line (hosted by the GCR Registry) to request contact from the study team regarding any concerns. Jointly, our research team includes 2 board-certified genetic counselors ([name], [name]), an oncologist ([name]) and a bioethicist ([name]) with expertise in areas that may raise concerns for participants. We can arrange call backs to participants who register concerns related to their participation in the study.

Participants who receive tele-genetic counseling will have the opportunity to have their questions/concerns related to genetic screening/testing addressed by the genetic counselors as is standard practice. All of the genetic counselor interns will have to complete at least one cancer rotation at the time of the study and they will receive clinical oversight by senior clinicians including Drs. [name], [name], and [name]. Each of these genetic counseling professionals have extensive experience in cancer genetics. During the online discussions (Aim 3), they will also be available to answer questions related to cancer care and genetic counseling via online written responses.

More detail about data security and participant confidentiality are described below in the Data Management and Monitoring and Confidentiality sections of this protocol.

6.3 *Describe the source records that will be used to collect data about participants. (Attach all surveys, scripts, and data collection forms in*

Smartform on “Study-Related Documents” page under “Other Attachments.” If unable to attach data collection instruments due to copyright requirements, include description of the instrument in the protocol document)

Aim 1: User testing procedures will include structured interviews to assess website content and messaging feedback, and the ratings of the website using the Suitability Assessment of Materials (SAM) and Comprehensibility (CAM) scale, facilitated by Peachtree Solutions (the developer of the website).

Aim 2: Primary data sources include: 1) GCR will record all survivor contacts (i.e., mailings, calls, messages left, call-backs), 2) website use reported by Peachtree Solutions on a monthly basis (i.e., website login and user-patterns data), 3) genetic counseling interns’ electronic case logbook of appointment scheduling and completion, 4) post-intervention online survey.

Aim 3: Data sources are online survey data and participants’ comments on the online discussion forums collected from the study website.

The project is currently in the process of being considered for funding by NCI. NIH requires provisional IRB approval for any project to receive funding. At this time there are no documents that are ready for IRB review. We state this throughout the protocol, that all documents will be submitted prior to interacting with study participants. We are asking that we obtain approval in concept for the project, provisional on review of specific materials if the grant is funded. We used the same approach for our Deliberative Democracy R21 (IRB00114524) that was funded in December, 2019.

6.4 What data, specifically, will be collected during the study and how that data will be obtained.

Primary RCT outcomes: 1) Survivor reach: the proportion of the eligible survivors identified and contacted by GCR who log in to the website, 2) Close relative reach: the proportion of close relatives enumerated by survivors who log in to the website, and 3) Uptake of cancer genetic services: the proportion of untested survivors who complete telegenetic counseling and the proportion of relatives enumerated who complete B-RST™ screening and subsequently access genetic counseling. We will evaluate secondary outcomes: In the MBI arm, we will track survivor’ and relatives’ patterns of website usage including: duration of time on the website, number of return visits, pages viewed, and the proportion of survivors who select different relative contact options. We can also link survivor and relative patterns of use to evaluate “family” patterns of use. We will assess the proportion of survivors and relatives who self-report in the post-intervention online survey (described below) having completed genetic testing, but we will not have sufficient power to consider uptake of genetic testing as a primary outcome.

Primary data sources include: 1) GCR will record all survivor contacts (i.e., mailings, calls, messages left, call-backs), 2) website use reported by Peachtree Solutions on a monthly basis (i.e., website login and user-patterns data), and 3) genetic counseling interns’ electronic case

logbook of appointment scheduling and completion. We will limit website data collection to information regarding survivor's prior genetic counseling/testing, enumeration of relatives, and contact information for relatives with survivors' approval to contact. We will limit data collected from relatives on the website to telephone number, home address, email addresses, and to prior experiences with genetic counseling/testing. We decided against a formal survey prior to or during the intervention to minimize participant burden and to enable a cleaner evaluation of the feasibility of using the proposed intervention to maximize survivor/relative reach.

Post-intervention online survey: We will recruit survivors and relatives who logged on to the website, regardless of their level of participation. We will post a study invitation letter and a one-time 20-minute survey on the study website and send the letter to survivors and relatives with contact information (e.g., mailing address, email, or mobile phone number) about 4 weeks after the intervention phase.

Based on our sample size scenarios in [Table 3](#) we estimate recruiting 120 survivors (15% response rate) and 66 relatives (15% response rate) to complete the online survey. We will compensate participants with \$35 to complete the online survey. In other research, we used an online survey to evaluate recall of B-RST™ results following a mammogram screening visit; 35% agreed to complete an online survey with a \$25 incentive.⁶³ We will include measures of ([Table 2](#)): Ability to process health information ("How confident are you filling out medical forms by yourself?") This item correlates strongly with longer health literacy assessments¹⁴²; We will assess central processing in several domains: a 7-item breast/ovarian cancer genetic knowledge scale¹⁴³, recall of the B-RST™ result (correct/incorrect), accuracy of perceived likelihood of carrying a *BRCA1/2* mutation, and accuracy of perceived absolute risk of ovarian cancer ("how likely is that you will develop ovarian cancer in your lifetime?").⁶³⁻⁶⁵ We will assess defensive processing with a 9-item information acceptance scale in which relatives respond to statements such as, "The information I received about my risk for hereditary breast and ovarian cancer seems accurate" (scores range from 0-45, a higher score indicates a high acceptance)⁶³. Cancer fear is based on 3-items (e.g., "of all the diseases, I am most afraid of cancer.")⁶⁶ We will assess comparative risk perception with a single item "compared to the average woman your age, would you say that you are less likely/as likely/more likely to develop ovarian cancer." Prevention efficacy: We will assess ovarian cancer fatalism with two items (e.g., "If a woman is meant to get ovarian cancer, she will get it no matter what she does?").⁶⁶ Other measures: cancer genetic testing (yes/no), extent of family discussions about ovarian cancer, and relevant demographics.³⁰

Table 2. Post-Intervention Online Survey Data Collection

Component	Measures
Ability to process health information	health literacy
Central processing	Breast/ovarian cancer knowledge, accuracy of perceived risk for BRCA1/2 mutations and ovarian cancer
Defensive processing	Accept information as accurate, cancer fear, cancer risk perception
Prevention efficacy	Endorsing statements that ovarian cancer risk can be reduced
Reactions to the intervention	Acceptability and votes on outreach communication approaches
Other	Family communication style, age, race, education, personal cancer history etc.

Process Data Collection and Measures: To measure reach (coverage and participation rates) and dosage (intervention delivered and received), we will electronically track the number of mailings/phone calls to each participant, website usage pattern, request for genetic counseling, and the completion of genetic counseling and testing. **Fidelity:** For quality control purposes, Drs. [name] and [name] will evaluate audio-recordings of ~70 sessions (10% of the estimated total) to assess whether the following topics have been discussed: personal/family medical history, inheritance, appropriate genetic tests, and the risks/benefits/limitations of recommended tests. A sum score of 80 (out of 100) will demonstrate good quality of counseling.

All survey instruments used in the study will be developed in the 12-month planning stage. Prior to fielding the study, these instruments and related scripts will be submitted as an IRB amendment.

6.5 If there are plans for long-term follow-up (once all research related procedures are complete), what data will be collected during this period.

- N/A.

6.6 If audio/video-recordings will be generated, describe processes for transcribing audio/video recordings. Will audio-recordings be destroyed after transcription? If so, how long after transcription? If not how will they be kept secure? If video-recordings will be used beyond the current research procedures for educational/presentation purposes.

- The genetic counseling sessions will be held on Zoom and the meetings will be recorded. After each session, all recorded files will be uploaded to Emory password protected, research network drives. The recordings will be deleted from any computers/laptops after transcription. Access will be given to essential team members only. No personal identifiable information will be transcribed or reported.
- For quality control purposes, Drs. [name] and [name] will evaluate recordings of ~70 sessions (10% of the estimated total) to assess whether the following topics have been discussed: personal/family medical history, inheritance, appropriate genetic tests, and the risks/benefits/limitations of recommended tests.

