B.3. Randomization: We will randomly assign cancer survivors (N=2,918) in a 1:1 ratio to either the MBI arm (n=1,459) or the waitlist standard outreach arm (n=1,459). Given our access to the entire population of ovarian cancer survivors in GA and characteristics of their cancer and treatment, we will use a covariate adaptive randomization procedure.^{43,44} In this procedure, we will randomly assign the first participants to a group, then will assign subsequent participants to a particular group by taking the covariates and previous assignment into account to adapt the probability of group assignment. This approach ensures our randomization is superior to simple randomization that only works perfectly for very large samples.⁴⁵ It will result in a covariance balanced allocation and thus avoid potential influence of covariates on the intervention results. We will use the SAS macro developed by Colavincenzo to execute the randomization.⁴⁶ We will choose covariates we expect are related to reach from the cancer registry data. Examples are year of diagnosis and age at diagnosis. Registry staff will randomize identified survivors to arm using sequentially numbered and sealed envelopes.

B.4. GCR Recruitment Procedures: The proposed recruitment procedures comply with GCR's current standards. We adapted them from strategies that were effective in other studies using cancer registry for recruitment^{34,39,42,47,48} that will allow for sustaining and disseminating the intervention beyond the study. We will classify survivors who log in to the study website as "reached." Recruitment will rely on multiple communications aimed to encourage survivors to log in to the study website with the number of contacts largely identical for both arms (Figure 4).

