B.4.1. First contact letter (MBI arm only): We will mail survivors in the MBI arm a one-page infographic (See "U01 MBI infographic draft") that includes a postage-paid return envelope to return their responses to three questions (See "U01 MBI three questions draft"). Responses will help us better understand information needs of families affected by ovarian cancer. Participants may answer the questions online by using a QR code, or write their responses on the enclosed document and return it to GCR. Responses will be anonymous and will not be linked to any personal identifiable information. We will not report participants' responses for research purposes and their responses will be reported on an aggregate level (e.g., number of envelopes returned).

[figure not shown]
B.4.2. First mail-out: This mailing will be sent approximately 7-10 days after mailing the first contact letter, we will mail to survivors in both arms \$5 cash as a token of appreciation for their attention, and a recruitment packet based on their arm assignment: targeted print material in the MBI arm versus standard study invitation letter in the standard outreach arm. GCR staff will mail recruitment materials in batches of about 172 every month. We will use Accurint, a LexisNexis database with coverage across the US, to obtain the most current address for registry survivors in an effort to maximize reach of the mailed material on the initial attempt. The materials will instruct participants to contact the toll-free registry telephone number with questions or concerns. Throughout recruitment, we will perform monthly checks to avoid

initiating contact with a recently deceased woman. To reduce unnecessary contact attempts by GCR, the intervention coordinator will provide GCR with the IDs of survivors who have logged in to the study website on a biweekly basis.

B.4.3. Telephone contacts: Studies show that interpersonal communications, such as a personal phone call, can increase clinical trial accrual when combined with informational handouts.⁴⁸⁻⁵³ Two weeks after mailing each packet, GCR will contact survivors by phone who do not log in to the study website. We will call survivors every 2-3 days for up to 9 attempts, after which we will categorize them as inaccessible. The phone call aims to: 1) check on receipt of the recruitment packet; 2) remind survivors to log in to the study website; and 3) answer questions regarding the study. This schedule is the standard for GCR outreach.

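### The protocol describes a covariate-adaptive macro and sequential sealed envelopes without connecting them, and states no arm blinding or common script for the registry's reminder calls that prompt log-in

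*Combined protocol and SAP*

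**What the plan says.** **Allocation (Section 6.1, B.3).** The plan is to assign 2,918 women 1:1, 1,459 per arm, and "we will use a covariate adaptive randomization procedure". After the first participants, each assignment is made by "taking the covariates and previous assignment into account to adapt the probability of group assignment", with a SAS macro named as the tool. Covariates will be chosen from registry data; year of diagnosis and age at diagnosis are given only as examples. The section then closes with "Registry staff will randomize identified survivors to arm using sequentially numbered and sealed envelopes". It does not say who runs the macro, when, or whether an envelope belongs to a particular survivor.

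**Contacts (B.4.2 and B.4.3).** Georgia Cancer Registry (GCR) staff mail packets that differ by arm, in batches of about 172 a month, with monthly checks for deaths. Two weeks after each packet, "GCR will contact survivors by phone who do not log in to the study website". Calls are made every 2 to 3 days for up to 9 attempts. One of their three stated aims is to prompt log-in, which defines survivor reach, a primary outcome (Section 4.1).

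**Blinding.** The only blinding statement concerns the counseling interns (B.5.1.c): "Interns will be blinded to" study arm. Nothing comparable is said of the registry's callers, and no trial call script is given.

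**The concern.** There are two separate issues.

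First, the two mechanisms in B.3 are different procedures. Covariate-adaptive allocation needs a woman's covariates and the running arm totals before it can produce her assignment. A numbered envelope opened in sequence holds an assignment that does not depend on who receives it. A reader cannot tell which procedure will be run or reproduce it. If it is the envelopes, the balance that B.3 claims is not what the trial will have. The survivor models in Section 17.0 name arm as the predictor and list no balancing covariates, so the plan leaves balance to the allocation.

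Second, the reminder call acts directly on a primary outcome. B.4.3 itself cites evidence that personal calls raise accrual. The registry as an organization holds the arm assignment, because its staff assign women and mail arm-specific packets. If callers know the arm, effort or content could differ between arms, and part of any difference in reach would come from the calls and not from the messages.

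**Working it through.** **Plan's own figure.** Table 3 gives power above .99 for survivor reach at 45% versus 10% with 1,459 per arm. The significance level is not stated; two-sided 0.05 is assumed here. Pooled rate = 0.275, SE = sqrt(2 × 0.275 × 0.725 / 1459) = 0.0165, and 0.35 / 0.0165 = 21 standard errors. Power is 1.000, so the figure reproduces. It does not depend on the allocation mechanism.

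**Cost of losing covariate balance.**
- For a covariate present in 50% of women and a 1:1 list that ignores it, SD of the arm difference = sqrt(2 × 0.25 / 1459) = 0.0185, about 1.9 points.
- Even if that covariate changed reach by 35 points, as much as the planned arm difference, a one-SD imbalance would move the estimated difference by 0.0185 × 35 = 0.65 points.
- Illustrative simulation (assumed: one 4-level and one 3-level covariate, biased coin 0.8, N = 2,918, 150 runs):

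| Allocation | Largest arm difference in any covariate level, mean | 95th percentile |
|---|---|---|
| Fixed 1:1 list | 2.7 points | 4.4 points |
| Minimization | 0.14 points | 0.24 points |

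The balance forgone is real but minor at this sample size.

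**What a caller effect would do.** The documents give no size for it. The number of women called is also not given: it is those not logged in two weeks after mailing, which exceeds the number who never log in. The calculation therefore assumes a net shift x in one arm's reach, with no true message effect. A shift of 2 points is 0.02 × 1459 = 29 women; 3 points is 0.03 × 1459 = 44 women.

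P(significant in that direction) = Φ[(x − 1.96 × SE0) / SE1], where SE0 uses the pooled rate and SE1 the two separate rates. At base 10% and x = 0.02: SE0 = sqrt(2 × 0.11 × 0.89 / 1459) = 0.01159, SE1 = sqrt((0.09 + 0.1056) / 1459) = 0.01158, and Φ[(0.02 − 0.0227) / 0.01158] = 0.41.

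| Base log-in | x = 1 point | 2 points | 3 points | 4 points |
|---|---|---|---|---|
| 10% | 14% | 41% | 72% | 91% |
| 20% | 10% | 26% | 51% | 74% |
| 30% | 9% | 21% | 42% | 64% |

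The nominal rate in one direction is 2.5%.

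**Against the planned differences.** Planned: 45 − 10 = 35 points, of which 2 to 3 points is 6% to 9%. Section 17.0 also considers 20% reach in the MBI arm: 20 − 10 = 10 points, of which 2 to 3 points is 20% to 30%.

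**The case against.** The best defense is that B.3 can be read coherently. The registry frame and its covariates are known in advance, and the macro is named as the tool that performs the randomization. It could be run over the list and each result sealed under one woman's ID, with the envelopes merely conveying it. That stands as a possibility. A reader might infer that envelopes can never deliver a covariate-adaptive allocation, and the text does not support that. What it supports is that the link is missing and that the closing sentence, as written, has staff randomizing with the envelopes.

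A reader might also infer that staff could steer assignments by choosing who takes the next number. Sequential numbering and sealing exist to conceal the next assignment, and nothing in the documents suggests the contents would be known. Nor do they say that allocation follows the monthly mailing batches or that envelopes pass between women.

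On the calls, both arms share one schedule and the same stated aims. GCR already records every mailing, call, message and call-back (Sections 6.3 and 6.4). Log-in is captured electronically by the website vendor, so callers do not record the outcome. All of this stands and rules out biased recording as the problem. It does not make call content or persistence equal between arms. That individual callers know the arm remains an inference: the documents do not say who within the registry calls or what the call list shows.

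**Conclusion.** The point holds in two limited parts.

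1. B.3 contains two unconnected allocation mechanisms. Unless envelopes are tied to survivor IDs after the macro has run, the stated balance is not delivered. This makes the procedure unreproducible as written; the statistical loss is small, with an SD of about 1.9 points on a 50% covariate. It does not affect the planned power or, by itself, bias the comparison.
2. The registry that assigns and mails by arm also makes the calls that prompt log-in, with no stated blinding or common script. The size of any effect is unknown. Under the assumed net shift of 2 to 3 points with no true message effect and 10% base log-in, a false positive would occur in about 41% to 72% of trials.

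It would be tempting to conclude that the calls could manufacture the trial's result. They could not produce the planned 35-point difference at that size. The exposure is to a small true difference, and it rests on callers knowing the arm and behaving differently, neither of which the documents establish. The point warrants a change because the protection is cheap, not because bias has been shown.

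**What to change.** **Allocation.** Replace the envelope sentence in B.3. Freeze the roster, or each batch file, after the vital-status and address checks. Run the macro centrally on named registry covariates, keeping a random element in each assignment, and return an allocation file keyed by survivor ID to mailing staff. This should be less work than preparing 2,918 envelopes.

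**Calls.** Omit arm from the call list, use one script common to both arms that refers neutrally to the study packet, and tabulate the already recorded call attempts by arm. The first two need a hidden field and a short document; the third needs only a table. No additional staff member for content questions is proposed.

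**Limits.** A caller may learn the arm if a woman describes her packet, so blinding will be incomplete. Section 13.0 refers to calls already made during trial recruitment. For women already allocated, the protocol should record which mechanism was actually used, and the tabulation of attempts by arm remains possible.
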